5.3 LIFESTYLE CONSIDERATIONS

Not applicable.

5.4 SCREEN FAILURES

Screen failures are defined as participants who consent to participate in the clinical trial but are not subsequently entered in the study. A minimal set of screen failure information is required to ensure transparent reporting of screen failure participants, to meet the Consolidated Standards of Reporting Trials (CONSORT) publishing requirements, and to respond to queries from regulatory authorities. Minimal information includes demography, screen failure details, eligibility criteria, and any serious adverse event (SAE).

6 STUDY INTERVENTION

6.1 DEVICE DESCRIPTION

The purpose of this instrument is to obtain optical measurements from the esophageal mucosa via an endoscopic probe. The imaging modalities used by this probe are angle-resolved Low-Coherence Interferometry (a/LCI), a technology that measures the depth- and angle-dependent scattering of light by tissue and Optical Coherence Tomography (OCT), a depth-resolved optical imaging technology. These optical readings provide indications of subsurface tissue architecture and will assist in the detection and diagnosis of metaplastic and dysplastic conditions such as Barrett's esophagus.

The probe is designed to be used in conjunction with the visual guidance provided by a commercial endoscope. The probe has mechanical features similar to a radiofrequency ablation (RFA) "paddle",

which is externally attached to an endoscope to provide ablative therapy under visual guidance of the endoscope. This form is advantageous because it is known to be well-tolerated and easily passed when mounted on the endoscope. It will also eventually allow the development of a single paddle that could both image and treat diseased mucosa.

Once inserted into a patient's esophagus and placed against the tissue surface, the probe will acquire 2D OCT images of the tissue surface at operator-selected locations. Some of the optical data received will be displayed in real-time. All optical data will also be stored on a computer for post hoc analysis.

The components of the combined probe system a/LCI-OCT instrument are grouped into the following modules: 1) Optical probe, 2) OCT engine, 3) a/LCI engine, 4) computer system, and 5) physical enclosure.

6.1.1 aCI/OCT OPTICAL PROBE

The optical probe is similar in form to a RFA "paddle," with a length of approximately 23 mm, width of 14 mm, and a thickness of 4 mm. The paddle housing is fabricated by a 3D printing process known as stereolithography (SLA). A miniature optical assembly for both a/LCI and OCT imaging is contained within the paddle, composed of silica and borosilicate glass, optical fiber, and optical adhesives. These components are fully enclosed within the paddle, except for the optical fiber, which extends from the paddle through a hollow sheath to the optical engine. The paddle and sheath are sealed against air and moisture to isolate the internal optical components from the patient environment. A transparent region of the paddle housing allows the beam to exit the paddle. Figure 1 below illustrates the general concept of the paddle probe attachment to the endoscope. Figure 2 depicts the probe layout within the paddle. (This figure is schematic and not to scale.)

The OCT modality components will rotate on command to sweep a beam across the tissue surface to generate 2D images, as well as translate longitudinally on command to generate 3D volumes. The speed of OCT rotation will be 40 rotations per second (2,400 rotations per minute) or less. The speed of OCT translation will be 2 mm per second or less.

[figure not shown]
[figure not shown]

Figure 1: 3D concept rendering of probe paddle attached to endoscope

Figure 2: Schematic for placement of optical probe components within paddle. Right, schematic of OCT optical component layout within OCT probe

To transduce its linear and rotational motion, a wound steel torque coil encloses the OCT optical fiber, which transmits force from motors mounted on the OCT engine to the OCT optical components within the paddle.

A flexible tether containing the OCT driveshaft and optical fiber protrudes from the proximal end of the probe, runs alongside the endoscope until it exits the body where it is connected to the OCT engine. The probe contains no electrical components or wires.

[figure not shown]

Figure 3: 3D drawing of paddle probe housing. This housing will contain miniature optics and will be attached to the tip of an upper GI endoscope via a silicone cuff (gray cylinder).

6.1.2 OCT ENGINE

The OCT engine contains the optical, electrical, and mechanical components related to the acquisition of OCT images from the esophagus.

The OCT system includes a light source (superluminescent diode, Exalos AG) emitting at approximately 1300 nm, a spectrometer composed of lenses and a diffraction grating, a sensor (linear array camera, Sensors Unlimited Inc.), a rotary motor system including a motor driver and belt assembly, a fiber-optic rotary junction (FORJ, Princtel), a translational motor system including a motor driver and translating stage, and various optical fibers, connectors, and controllers.

In brief, the OCT light source transmits light that is simultaneously divided among two paths: a static reflector within the OCT engine (“reference” light) and a path directed towards the patient tissue via the probe (“sample” light). The FORJ allows the probe fiber to rotate relative to the stationary fiber while remaining optically connected. The light from both sample and reference paths are recombined by a fiber coupler, resulting in an interference pattern that encodes the depth of reflective objects and surfaces in the sample. This interference is detected by a spectrometer, which divides the interference signal into its constituent wavelengths that are individually detected by pixels of a linear camera. Figure 4 below depicts the block diagram of the OCT engine.

[figure not shown]

Figure 4: Block diagram of OCT engine components

Each such measurement produces a column of data, or “A-scan,” which represents the depth-resolved reflectance profile of the tissue where the OCT beam intersects it. To produce 2D OCT images, the miniature optics in the probe are rotated by the rotary motor and FORJ system, which are mechanically linked by a belt system and the wound-steel torque coil within the probe sheath. To produce 3D OCT images, a stage is translated by a stepper motor such that the entire fiber optic assembly moves longitudinally during its rotation, resulting in a spiral scan.

The maximum permissible exposure (MPE) for exposures greater than 10 seconds on skin is 1.0 W/cm^2 at the principal OCT wavelength of 1300 nm and a defined limiting aperture of 3.5 mm diameter (ANSI Z136.1). The OCT beam focus falls entirely within the 3.5 mm (0.35 cm) aperture, and thus is the power limit is $1.0 \text{ W/cm}^2 * 3.14 * (0.175 \text{ cm})^2 = 96.2 \text{ mW}$. The total power of OCT beam on the tissue is less than 20 mW.

6.1.3 A/LCI ENGINE

The a/LCI engine contains the optical, electrical, and mechanical components related to the acquisition of a/LCI images from the esophagus. a/LCI, uses the pattern of scattered light to measure the size of nuclei within the epithelium, which is a known biomarker for dysplasia.

The a/LCI engine is very similar to the OCT engine in terms of the diagrammatic modules that compose the system, operating in parallel with the OCT engine.

The a/LCI engine includes a light source (superluminescent diode, Superlum) emitting at approximately 830 nm, a spectrometer composed of lenses and a diffraction grating, a sensor (area camera, FLIR Imaging), and various optics that compose the interferometer. The interferometer sends light to the probe via an optical fiber, collects the scattered light returning from the probe's optical fiber bundle, and combines that sample light with reference light to be detected on the camera.

The maximum permissible exposure (MPE) for exposures greater than 10 seconds on skin is 3.6 mW/mm² at our principal wavelength of 830 nm (ANSI Z136.1). Our imaging region in the tissue is approximately 100 μ m, smaller than the minimum limiting aperture given in ANSI Z136.1 of 3.5 mm. Our total permissible power is thus $3.6 \text{ mW/mm}^2 \times 3.14 \times (1.75 \text{ mm})^2 = 34.6 \text{ mW}$. Our maximum power of 10 mW is much lower than the ANSI MPE.

6.1.4 A/LCI OPTICAL PROBE

The optical probe is similar in form to a RFA "paddle," with a length of approximately 23 mm, width of 14 mm, and a thickness of 4 mm. The paddle housing is fabricated by a 3D printing process known as stereolithography (SLA). Miniature optical assembly for a/LCI is contained within the paddle, composed of silica and borosilicate glass, optical fibers, and optical adhesives. These components are fully enclosed within the paddle, except for the optical fibers, which extend from the paddle through a hollow sheath to the a/LCI optical engine. The paddle and sheath are sealed against air and moisture to isolate the internal optical components from the patient environment. Transparent window regions of the paddle housing allow the a/LCI beam to exit the paddle.

Upon identification of an area of interest on the esophagus, based on video endoscopy and/or the OCT images, an a/LCI acquisition will be initiated. This component does not entail moving parts in the probe, but engages a series of optical acquisitions lasting less than 10 seconds while the probe is held in place. A flexible tube containing the OCT driveshaft and optical fiber protrudes from the proximal end of the probe, runs alongside the endoscope until it exits the body where it is connected to the OCT engine. A second tube containing the a/LCI illumination and detection fibers runs parallel to the first. Both tubes are tethered together in a single outer tubing, composed of polyolefin. The probe contains no electrical components or wires.

6.1.5 A/LCI-OCT ENGINE

The combined a/LCI-OCT engine will operate both systems in tandem. Individual components have been previously described in Section 6.1.2 and 6.1.3. Figure 5 below depicts the block diagram of combined a/LCI-OCT engine.

[figure not shown]

Figure 5: Block diagram of combined a/LCI and OCT engine components.

6.1.6 COMPUTER

A computer workstation performs the data acquisition and control through a custom application. Software control of the data acquisition sequence is provided. Real-time display of the OCT and a/LCI data is shown on a monitor. Raw and/or processed OCT image data and a/LCI data are saved to the hard drive. Storage of patient data on the computer is protected by encryption (Bitlocker).

6.1.7 PHYSICAL ENCLOSURE AND POWER BUS

The a/LCI and OCT engine and computer are contained within a painted and grounded aluminum enclosure. An isolated 120V power bus is connected through a medical isolation transformer, which provides power to all electrical components.

6.2 NON-SIGNIFICANT RISK (NSR)

6.2.1 NSR JUSTIFICATION

The FDA defines an NSR device as one which does not meet the definition of a significant risk (SR) device. Per 21 CFR 812.3(m), a Significant Risk Device is an investigational device that:

- Is intended as an implant and presents a potential for serious risk to the health, safety, or welfare of a subject;

- b. Is purported or represented to be for use supporting or sustaining human life and presents a potential for serious risk to the health, safety, or welfare of a subject;
- c. Is for a use of substantial importance in diagnosing, curing, mitigating, or treating disease, or otherwise preventing impairment of human health and presents a potential for serious risk to the health, safety, or welfare of a subject; or
- d. Otherwise presents a potential for serious risk to the health, safety, or welfare of a subject.

This device is (a) not intended as an implant, (b) is not used to support or sustain life, (c) is not for a use of substantial importance in diagnosing, curing, mitigating, or treating disease, or otherwise preventing impairment of human health and presents a potential for serious risk to the health, safety, or welfare of a subject; and (d) does not otherwise present a potential for serious risk to the health, safety, or welfare of a subject.

In fact, the FDA guidance document titled “Information Sheet Guidance for IRBs, Clinical Investigators, and Sponsors: Significant Risk and Nonsignificant Risk Medical Device Studies,” specifically cites gastroenterology and urology endoscopes and accessories as examples of non-significant risk devices (Section X, subpart A, page 8).

6.2.2 NSR COMPLIANCE

The device used in this study may be deemed a non-significant risk (NSR) device by the IRB or FDA. If deemed an NSR, this means the device qualifies for an abbreviated investigational device exemption (IDE). To qualify as an NSR, the FDA or IRB must determine the device does not pose a serious risk to the health, safety or welfare of a subject and does not otherwise meet the definition of a significant risk device according to 21 CFR 812.3(m). If deemed non-significant risk (NSR); the sponsor and investigator must comply with "abbreviated IDE requirements" described in 21CFR812.

Subpart A--General Provisions

§ 812.1 - Scope.

§ 812.2 - Applicability.

§ 812.3 - Definitions.

§ 812.5 - Labeling of investigational devices.

§ 812.7 - Prohibition of promotion and other practices.

§ 812.10 - Waivers.

§ 812.18 - Import and export requirements.

§ 812.19 - Address for IDE correspondence.

Subpart B--Application and Administrative Action

§ 812.20 - Application.

§ 812.25 - Investigational plan.

§ 812.27 - Report of prior investigations.

§ 812.30 - FDA action on applications.

§ 812.35 - Supplemental applications.

§ 812.36 - Treatment use of an investigational device.

§ 812.38 - Confidentiality of data and information.

Subpart C--Responsibilities of Sponsors

§ 812.40 - General responsibilities of sponsors.

§ 812.42 - FDA and IRB approval.

§ 812.43 - Selecting investigators and monitors.

§ 812.45 - Informing investigators.

§ 812.46 - Monitoring investigations.

§ 812.47 - Emergency research under 50.24 of this chapter.

Subpart D-IRB Review and Approval

§ 812.60 - IRB composition, duties, and functions.

§ 812.62 - IRB approval.

§ 812.64 - IRB's continuing review.

§ 812.65 - [Reserved]

§ 812.66 - Significant risk device determinations.

Subpart E--Responsibilities of Investigators

§ 812.100 - General responsibilities of investigators.

§ 812.110 - Specific responsibilities of investigators.

§ 812.119 - Disqualification of a clinical investigator.

Subpart F [Reserved]

Subpart G-Records and Reports

§ 812.140 - Records.

§ 812.145 - Inspections.

§ 812.150 - Reports.

<https://www.accessdata.fda.gov/scripts/cdrh/cfdocs/cfcfr/CFRSearch.cfm?CFRPart=812>

6.3 PREPARATION/HANDLING/STORAGE/ACCOUNTABILITY

6.3.1 ACQUISITION AND ACCOUNTABILITY

The devices listed in this protocol will be manufactured by the co-PI, [name], at Duke University and provided to UNC Chapel Hill for use in this pilot study. Accountability logs will be maintained by both Duke University and UNC Chapel Hill.

6.3.2 DEVICE LABELING

The device will be labeled with a serial number, and in accordance with 21CFR812.5 (below):

(a) Contents. An investigational device or its immediate package shall bear a label with the following information: the name and place of business of the manufacturer, packer, or distributor (in accordance with §801.1), the quantity of contents, if appropriate, and the following statement: "CAUTION—Investigational device. Limited by Federal (or United States) law to investigational use." The label or other labeling shall describe all relevant contraindications, hazards, adverse effects, interfering substances or devices, warnings, and precautions.

(b) Prohibitions. The labeling of an investigational device shall not bear any statement that is false or misleading in any particular and shall not represent that the device is safe or effective for the purposes for which it is being investigated.

(c) Animal research. An investigational device shipped solely for research on or with laboratory animals shall bear on its label the following statement: "CAUTION—Device for investigational use in laboratory animals or other tests that do not involve human subjects."

(d) The appropriate FDA Center Director, according to the procedures set forth in §801.128 or §809.11 of this chapter, may grant an exception or alternative to the provisions in paragraphs (a) and (c) of this section, to the extent that these provisions are not explicitly required by statute, for specified lots, batches, or other units of a device that are or will be included in the Strategic National Stockpile.

6.3.3 DEVICE STORAGE

The device(s) will be stored in a secure location with access limited to research personnel.

6.3.4 PREPARATION

Prior to each use, the device will be cleaned per current clinically approved methods for disinfecting endoscopy equipment which will utilize Cidex and/or Revital-Ox. Disinfection methods for this study have been reviewed and approved by the UNC Hospitals outpatient care and instrument reprocessing group. Refer to study standard operating procedures for additional information.

6.4 CONCOMITANT THERAPY

There are no medication restrictions to participate in this study other than the standard of care medication discontinuation instructions patients receive in preparation for an upper endoscopy.

6.4.1 RESCUE MEDICINE

Not applicable.

7 STUDY INTERVENTION DISCONTINUATION AND PARTICIPANT DISCONTINUATION/WITHDRAWAL

7.1 STRATEGIES FOR RECRUITMENT AND RETENTION

All participants will be screened and enrolled using IRB-approved and HIPAA compliant methods. IRB approved site personnel will obtain consent prior to completion of any study procedures. Potential subjects will have an opportunity to carefully review the consent form. The details of the study will be reviewed verbally, and all questions will be answered to the satisfaction of the patient. After the subject signs the consent, a copy of the signed consent will be provided to the subject. The consent process will be documented.

7.2 PARTICIPANT DISCONTINUATION/WITHDRAWAL FROM THE STUDY

This is a pilot study involving one-time collection of data during a routine care endoscopy. Participants are free to withdraw from participation in the study at any time upon request.

An investigator may discontinue or withdraw a participant from the study if the participant is deemed ineligible based on findings from the endoscopy, or other reason.

The reason for participant discontinuation or withdrawal from the study will be recorded on the Case Report Form (CRF). Subjects who sign the informed consent form and are withdrawn may be replaced.

Withdrawn or terminated subjects will be excluded from the study. If data were collected, then they will not be used.

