7.3 LOST TO FOLLOW-UP

This pilot study involves a one-time visit with data collection. However, if for some reason a subject needs to be contacted for follow-up, then a participant will be considered lost to follow-up if he or she fails to return for a scheduled visit and is unable to be contacted by the study site staff.

The following actions must be taken if a participant fails to return to the clinic for a required study visit:

- The site will attempt to contact the participant and reschedule the missed visit and counsel the participant on the importance of maintaining the assigned visit schedule and ascertain if the participant wishes to and/or should continue in the study.
- Before a participant is deemed lost to follow-up, the investigator or designee will make every effort to regain contact with the participant (where possible, 3 telephone calls and, if necessary, a certified letter to the participant's last known mailing address or local equivalent methods). These contact attempts should be documented in the participant's medical record or study file.
- Should the participant continue to be unreachable, he or she will be considered to have withdrawn from the study with a primary reason of lost to follow-up.

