8.2.5 TIME PERIOD AND FREQUENCY FOR EVENT ASSESSMENT AND FOLLOW-UP

The occurrence of an adverse event (AE) or serious adverse event (SAE) may come to the attention of study personnel during study visits and interviews of a study participant presenting for medical care, or upon review by a study monitor.

All AEs will be captured on the appropriate case report form (CRF). Information to be collected includes event description, time of onset, clinician's assessment of severity, relationship to study device (assessed only by those with the training and authority to make a diagnosis), and time of resolution/stabilization of the event. All AEs occurring while on study must be documented appropriately regardless of relationship. All AEs will be followed to adequate resolution.

Any medical condition that is present at the time that the participant is screened will be considered as baseline and not reported as an AE. However, if the study participant's condition deteriorates at any time during the study, it will be recorded as an AE.

Changes in the severity of an AE will be documented to allow an assessment of the duration of the event at each level of severity to be performed. AEs characterized as intermittent require documentation of onset and duration of each episode.

Research staff will record all adverse events with start dates occurring any time after informed consent is obtained until completion of study participation. At each study visit, the investigator will inquire about the occurrence of AE/SAEs since the last visit. Events will be followed for outcome information until resolution or stabilization.

All new or worsening adverse events (AEs) will be collected for all subjects from the time of subject enrollment through completion or termination of the clinical investigation. This includes AEs that are not device or procedure related.

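### Section 7.2 bars the use of all data from withdrawn subjects with no safety exception, so adverse events already recorded in them are left out of any tabulated rate

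*Combined protocol and SAP*

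**What the plan says.** Four parts of the combined protocol and SAP bear on this point.

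- **Withdrawal (7.2).** The rule is "Withdrawn or terminated subjects will be excluded from the study. If data were collected, then they will not be used". Subjects may leave at their own request. The investigator may also withdraw a subject "if the participant is deemed ineligible based on findings from the endoscopy, or other reason". On replacement: "Subjects who sign the informed consent form and are withdrawn may be replaced".
- **Loss to follow-up (7.3).** When contact attempts fail, "he or she will be considered to have withdrawn from the study with a primary reason of lost to follow-up".
- **Analysis population (9.3).** There is one population, described as serving device optimization. It takes in everyone given the probe, in either cohort, except those withdrawn under 7.2. No safety population is defined.
- **AE recording (8.2.5).** "All AEs occurring while on study must be documented appropriately regardless of relationship". One paragraph starts recording at informed consent. The next says that new or worsening AEs are "collected for all subjects from the time of subject enrollment through completion or termination of the clinical investigation".

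Section 9.1 promises 95% confidence intervals for all estimates and lists incidence rates among its examples, without naming an AE rate or a denominator.

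**The concern.** Withdrawal can follow from the outcome being measured. A subject who tolerates the probe badly is more likely than others to ask to stop, or to be withdrawn under the open-ended last ground in 7.2. Sections 7.2 and 9.3 together then take that subject's AEs out of the analysis, and replacement brings in another subject. An AE rate computed this way describes those who stayed in the study, not those exposed to the device.

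At stake is what this pilot can say about tolerability. Section 2.3.2 looks ahead to the imaging being shown safe and well tolerated. Sections 2.3.1 and 8.2.4.3 make the frequency of an event part of deciding whether it is expected. Both uses need a rate whose denominator is everyone exposed.

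**Working it through.** The documents give no AE rate, withdrawal rate or count of failed insertions, so there is no plan figure to reproduce. The check is mainly a reading of the text, followed by an illustration of scale.

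**Step 1: follow one subject through the text.** The subject consents, the probe is passed, and a non-serious AE is recorded.

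1. Recording: 8.2.5 requires the AE to be documented, whatever its cause.
2. Review: 8.2.6 and 10.1.6 send it to the independent safety monitor, the IRB and the NIH.
3. The subject then withdraws, or is withdrawn by the investigator. Section 7.2 now forbids use of the data.
4. Alternatively, the subject cannot be reached afterwards. The day-7 contact in 8.1.3 is the only planned contact after the procedure. The text of 7.3 is written around a missed visit, but the natural reading covers this contact, and it classes the subject as withdrawn. The procedure-day AE falls under 7.2 as well.
5. Analysis: 9.3 excludes the subject, and no other population restores the data.

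**Step 2: scale.** Inputs: 82 retained subjects (the planned total in 9.2, which replacement can preserve) and *w* removed subjects on top. The value of *w* and both AE rates are assumptions. With rate *p*₁ in retained and *p*₂ in removed subjects:

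rate in all exposed = (82·*p*₁ + *w*·*p*₂) / (82 + *w*)

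With *p*₁ = 5%, the reported rate is 5.0% throughout, and 82 × 0.05 = 4.1.

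| *w* | *p*₂ = 5% | *p*₂ = 25% | *p*₂ = 50% | *p*₂ = 100% |
|---|---|---|---|---|
| 4 | 5.0% | 5.1/86 = 5.9% | 6.1/86 = 7.1% | 8.1/86 = 9.4% |
| 8 | 5.0% | 6.1/90 = 6.8% | 8.1/90 = 9.0% | 12.1/90 = 13.4% |
| 16 | 5.0% | 8.1/98 = 8.3% | 12.1/98 = 12.3% | 20.1/98 = 20.5% |

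At the extreme of no events in retained subjects, exact Clopper-Pearson 95% intervals are:

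- as written, 0/82: 0 to 4.4% (upper limit 1 − 0.025^(1/82) = 0.044);
- with four removed subjects who each had an AE, 4/86 = 4.7%: 1.3% to 11.5%.

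If removed and retained subjects share one AE rate, there is no bias. The understatement appears only when AEs cluster in those removed.

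**Step 3: the two start points in 8.2.5.** Sections 8.1.2 and 9.3 define an enrolled subject as one given the device successfully and with evaluable data. Read with that definition, a start at enrollment would leave out an event during a failed insertion, while a start at consent would include it. The schedule of activities marks AE review at Screening, which agrees with consent.

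**The case against.** Much can be said on the other side.

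- **Recording and use are different things.** Section 8.2.5 governs recording and 7.2 governs use, so the two do not strictly contradict each other. Nor is any AE hidden from oversight: 8.2.6, 8.3.2, 8.3.3 and 10.1.6 keep review and reporting in place, and 7.2 records the reason for withdrawal. All of this stands. It confines the point to the analysis.
- **No AE analysis is specified.** The synopsis lists no endpoints, no objective concerns safety, and 9.4 plans only tissue-classification tables. This also stands. The flaw affects whatever AE rate is tabulated under the general wording of 9.1.
- **A stopped procedure is not a withdrawal.** Correct: under 9.3, a subject given the probe and not withdrawn stays in. But 7.2 allows withdrawal on request or at the investigator's discretion, so the route is open.
- **The start-point conflict may be only verbal.** The schedule also uses Enrollment as a visit name, so 8.2.5 need not mean the outcome-based definition. That is possible, and is a reason to settle the wording.

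Three stronger readings are tempting but unsupported. A reader might infer that 5.4 cuts the safety data of failed attempts down to serious events. It sets a minimum, "Minimal information includes demography, screen failure details, eligibility criteria, and any serious adverse event (SAE", and discards nothing. Its definition, "Screen failures are defined as participants who consent to participate in the clinical trial but are not subsequently entered in the study", is nowhere equated with failing the enrolled definition in 8.1.2. A reader might also take terminated subjects in 7.2 to include everyone affected if the study itself is stopped. That section concerns individual participants, and 10.1.2, on study closure, discards no data. Finally, one might conclude that the AE rates would describe mainly trouble-free procedures. Nothing in the documents shows how many subjects would be removed or how many of them would have had events.

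**Conclusion.** The point holds for the analysis of safety data. Sections 7.2, 7.3 and 9.3 together leave recorded AEs in withdrawn, terminated or lost subjects out of any tabulated rate, and no safety population brings them back. The likely direction is understatement, on the assumption that AEs are more frequent in those removed than in those kept.

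The size cannot be derived. In the illustration, a reported 5.0% stands against 5.9% to 20.5% for 4 to 16 removed subjects with AE rates of 25% to 100%, and against 5.0% if their rate is no different. The comparison of 0/82 with 4/86 is an extreme: section 2.3.1 lists sore throat and bloating among expected events, so no events at all in 82 subjects is unlikely. The change should be made because the rule depends on outcome and costs little to correct. Oversight of individual events is not in question.

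**What to change.** - **7.2:** limit the exclusion to imaging and performance data. State that AE and device-event data collected up to withdrawal, termination or loss to follow-up are retained and reported.
- **9.3:** add a safety population of all subjects in whom probe insertion was attempted, as the denominator for procedure-day AE rates. Report day-7 AEs among subjects actually contacted, with that number shown, because 8.1.3 does not contact non-enrolled subjects and the two denominators should not be mixed.
- **8.2.5:** keep one start point, informed consent, in line with the AE review at Screening in the schedule of activities.

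The cost is wording in three sections, with no new visits or procedures. The consent form is not among the documents reviewed, so its text on data kept after withdrawal should be checked against the revised 7.2. The one downside is that the reported AE rate may be slightly less favourable.
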